10.1 HVTN CRS laboratory procedures

The HVTN 116 Site Lab Instructions provide further guidelines for operational issues concerning the clinical and processing laboratories. This document includes guidelines for general specimen collection, special considerations for phlebotomy, specimen labeling, whole blood processing, HIV screening/diagnostic testing, and general screening and safety testing.

Tube types for blood collection are specified in [Appendix H](#), [Appendix I](#), [Appendix J](#), and [Appendix K](#). For tests performed locally, the local lab may assign appropriate tube types.

In specific situations, the blood collection tubes may be redirected to another laboratory or may require study-specific processing techniques. In these cases, laboratory special instructions will be posted on the protocol-specific section of the HVTN website.

10.2 Total blood volume

Required blood volumes per visit are shown in [Appendix H](#), [Appendix I](#), [Appendix J](#), and [Appendix K](#). Not shown is any additional blood volume that would be required if a safety lab needs to be repeated, or if a serum pregnancy test needs to be performed, in which case, additional blood volume would likely be minimal. The total blood volume drawn for each participant will not exceed 500 mL in any 56-day (8-week) period (includes estimated maximal blood loss associated with the biopsy procedures).

10.3 Drug detection and quantitation

10.3.1 VRC01/VRC01LS mAb levels in serum, mucosal tissue lysates and mucosal secretions

VRC01/VRC01LS levels will be measured in serum, semen, cervicovaginal secretions, rectal secretions, and mucosal tissue lysates prepared from cervical, vaginal and rectal biopsies collected at the designated timepoints. A quantitative assay (such as an ELISA), binding multiplex antibody assay (BAMA), or Singulex assay may be used to determine the concentration of VRC01/VRC01LS in the aforementioned samples and/or to assess their binding to various Env proteins, such as Consensus gp120, Consensus gp140 and CD4 binding site proteins. ELISA assays employing two different antigens may be used for VRC01/VRC01LS quantitation. One assay employs the resurfaced core 3 antigen (RSC3), designed for selective detection of CD4 binding site bNAbs, such as VRC01/VRC01LS (46). The other assay employs the VRC01 Fab-specific 5C9

mAb, which is an anti-idiotypic antibody cloned from a single B cell that was sorted by flow cytometry using a VRC01 scFv probe. The operational sensitivity of the BAMA and ELISAs with respect to the various sample specimens will be determined for the clinical grade VRC01/VRC01LS mAbs used for this study. However, ongoing studies currently indicate that the interim lower LOD for VRC01 mAb is $\leq 129 \pm 30$ ng/ml, 125 ± 22 ng/ml, and 93 ± 14 ng/ml in serum, semen, and saliva, respectively, using RSC3 protein on the BAMA platform (with validated plasma LOD of 2.3 -8.0 ng/ml). The LOQ of the validated ELISA using the VRC01 Fab-specific 5C9 mAb is currently 1.1 mcg/mL in serum. The Singulex assay combines a proprietary digital Single Molecule Counting (SMC) technology with a robust microparticle-based immunoassay utilizing the mAb 5C9 to provide higher sensitivity (lower limit of quantification = 50 pg/mL) and broad dynamic range. As the technology for all of these assays continues to develop, an updated assay(s) may be utilized. Any assay that may be used for this study will first be qualified, at a minimum, for linearity, precision, and accuracy.

10.3.2 Immunohistochemistry

The presence of VRC01/VRC01LS and its distribution in cervical, vaginal and rectal tissue will be assessed using immunohistochemical (IHC) methods employing biotinylated versions of mAb 5C9 or RSC3, on optimum cutting temperature (OCT) medium or paraffin embedded biopsies collected at the designated timepoints. The distribution of VRC01/VRC01LS will be described qualitatively or semi-quantitatively relative to the mucosal epithelium, stroma and/or lamina propria. The assay has been used to assess the distribution VRC01/VRC01LS in mucosal tissues from NHP infused with these mAbs and is being adapted for use with human mucosal tissues. As the technology for this assay continues to develop, updated versions may be utilized.

To assess the immunological and inflammatory milieu within which the infused mAbs are found (or not) in the cervical, vaginal and/or rectal compartments, additional IHC assays may be utilized. These assays may include the detection of various Fc receptors, including FcRn, effector cell/inflammatory cell infiltrates and other markers of local inflammation.

10.4 Drug functionality

10.4.1 Infectivity assay

Cervical, vaginal and rectal biopsies will be used to assess the protection provided by VRC01 and VRC01LS at different timepoints post infection. The assay uses immediate challenge of the biopsy tissue *ex vivo*. Currently, the assay measures luminescence from nanoluciferase as a readout of viral replication kinetics in the tissue explant.

We may use several challenge viruses with differential susceptibility to VRC01 neutralization, and may conduct the infection assay in the presence of the participant's serum to explore if serum antibody levels can be protective.

10.4.2 Anti-VRC01/VRC01LS antibody assay

Assessment for development of anti-VRC01/VRC01LS antibodies in subjects will be performed using the Meso Scale Discovery (MSD) platform based on electrochemiluminescence. Serial dilutions of sera/plasma samples are incubated with optimized concentrations of biotinylated VRC01 and SULFO-TAG labeled VRC01 at 2-8°C overnight. Samples are transferred to a Biotin-coated MSD plate and incubated for 1 hour at room temperature. Samples are read with the MSD-2400 with end point dilutions defined as the greatest sample dilution with a response above the positivity threshold for the assay. This assay is independent of the anti-VRC01 antibody isotype, and permits the detection of both high and low affinity antibodies.

The same assay format will be utilized for anti-VRC01LS, with reagents specific for that protein.

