Initial analyses were generated including VRC01 serum levels up to the day 168 visit. The trough level in Group 1 reached an average of 75.6 (64.6, 88.5) ug/ml before the second infusion (day 28), then decreased to trough levels of 50.7 (43, 59.8), 43.4 (36.8, 51.2), 37.3 (26.7, 52.1), and 31.7 (19.9, 50.3), prior to the 3rd (day 56), 4th (day 84), 5th (day 112), and 6th (day 140) infusions, respectively. The last measured level, 28 days after the 6th infusion, was 39.7 (28, 56.3) ug/ml. In Group 2, the trough levels, measured before the second (day 56) and third (day 112) infusions, averaged 20.1 (16.4, 24.6) ug/ml and 21.4 (15.7, 29.2) ug/ml, respectively. The last trough level observation, 28 days after the 3rd infusion, measured 15.1 (6.5, 35.3) ug/ml. In Group 3 (including placebo recipients), the trough levels, measured right before each subsequent 2-weekly SC injection, decreased steadily from 27.7 (8.8, 87.7) ug/ml at day 28 to 8.2 (2.6, 26.3) ug/ml at day 154. The last trough measurement at 14 days after the SC injection was 6 (1.9, 19.3) ug/ml. In Group 4, the trough levels, measured before the second (day 56) and third (day 112) infusions, averaged 4.1 (3.1, 5.3) ug/ml and 2.5 (0.8, 7.9) ug/ml, respectively. The last trough level observation, 28 days after the 3rd infusion, measured 4.2 (1.6, 11.4) ug/ml. In Group 5, the trough levels, measured before the second (day 56) and third (day 112) infusions, averaged 10.4 (6.8, 16.1) ug/ml and 11.5 (7.5, 17.5) ug/ml, respectively. The last trough level observation, 28 days after the 3rd infusion, measured 11.9 (3.8, 38) ug/ml. VRC01 serum levels for Group 4 and Group 5, which use the same doses as HVTN 116, ie VRC01 10mg/kg and 30mg/kg at two month intervals respectively, are shown in [Figure 4-6](#) and [Figure 4-7](#).

[figure not shown]

Figure 4-6 VRC01 serum levels in the HVTN 104 per-protocol analysis for Group 4.

[figure not shown]

Figure 4-7 VRC01 serum levels in the HVTN 104 per-protocol analysis for Group 5.

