Week:							W-2	W0	W1-2	W5-6	W8	W9-10	W12	W13-14	W15-16	W16	W19-20	W24	W25-26	W29-30	W37-38	W51-52	W64-65	W76-77	
BLOOD COLLECTION																									
Screening/Diagnostic																									
Screening HIV test	Local lab	Local lab	SST	5mL	5	—	—	—	—	—	—	—	—	—	—	—	—	—	—	—	—	—	—	—	5
HBsAg/anti-HCV	Local lab	Local lab	SST	5mL	5	—	—	—	—	—	—	—	—	—	—	—	—	—	—	—	—	—	—	—	5
HSV-1/2	Local lab	Local lab	SST	5mL	—	5	—	—	—	—	—	—	—	—	—	—	—	—	—	—	—	—	—	—	5
HIV diagnostics ⁵	UW-VSL/ HSM-LNICD	UW-VSL/ HSM-LNICD	EDTA	10mL	—	—	—	—	—	—	—	—	—	—	—	—	—	—	10	—	10	20	—	—	40
Safety Labs²¹																									
CBC/ Diff / platelets	Local lab	Local lab	EDTA	5mL	5	—	—	5	—	—	5	—	—	—	—	5	—	5	—	5	—	—	—	—	30
Chemistry panel ⁵	Local lab	Local lab	SST	5mL	5	—	—	5	—	—	5	—	—	—	—	5	—	5	—	5	—	—	—	—	30
Hormone Levels																									
Hormone panel ¹⁸	Local lab	Local lab	SST	8.5mL	—	8.5	—	—	—	—	—	—	—	—	—	—	—	8.5	8.5	8.5	8.5	—	—	—	43
STI Serology																									
Syphilis ¹⁰	Local lab	Local lab	SST	5mL	5	—	—	—	—	—	—	—	—	—	—	—	—	—	—	—	—	—	—	—	5
Drug Levels/Detection																									
VRC01 Ab levels	CSR	NVITAL/FHCRC	SST	8.5mL	—	y	—	y	y	y	y	—	—	y	—	y	y	y	y	y	y	y	—	—	0
Immunogenicity Assays																									
Host genetics ⁶	CSR	FHCRC	ACD	8.5mL	—	z	—	—	—	—	—	—	—	—	—	—	—	—	—	—	—	—	—	—	0
Anti-VRC01 Ab levels	CSR	VRC/NVITAL	SST	8.5mL	—	y	—	—	—	—	—	—	—	—	—	—	—	—	y	—	—	y	—	—	0
Functional humoral assays ⁹	CSR	Duke	SST	8.5mL	—	y	—	y	y	—	y	—	—	y	—	—	y	y	y	y	y	y	—	—	0
STORAGE																									
Serum storage	CSR	—	SST	8.5mL	—	76.5	—	51	51	8.5	51	—	—	51	—	8.5	51	8.5	51	51	51	51	—	—	561
PBMC storage	CSR	—	ACD	8.5mL	—	51 ^W	—	—	—	—	34 ^W	—	—	—	—	—	—	—	—	—	—	34 ^W	—	—	153
Visit total					25	151	0	61	51	9	95	0	51	0	9	95	9	90	70	90	124	0	0	927	
56-Day total¹⁶					25	176	176	237	288	121	216	155	206	206	163	250	112	193	263	159	124	0	0		
URINE COLLECTION																									
Urine dipstick ^{17,21}	Local lab	Local lab			X	—	—	X	—	—	—	—	—	—	—	—	—	—	—	—	X	—	—	—	—
Pregnancy Test ^{17,21}	Local lab	Local lab			X	X	X	X	X	X	X	—	—	X	—	X	X	X	X	X	X	X	—	—	—
Chlamydia/Gonorrhea ¹¹	Local lab	Local lab			X	—	—	—	—	—	—	—	—	X	—	—	—	—	X	—	—	X	—	—	—
RECTAL SWAB COLLECTION																									
Chlamydia/Gonorrhea ¹¹	Local lab	Local lab			X	—	—	—	—	—	—	—	—	X	—	—	—	—	X	—	—	X	—	—	—
CERVICAL/VAGINAL SWAB COLLECTION																									
Chlamydia/Gonorrhea ¹¹	Local lab	Local lab			X	—	—	—	—	—	—	—	—	X	—	—	—	—	X	—	—	X	—	—	—

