⁴ Local labs may assign appropriate alternative tube types for locally performed tests.

⁵ Chemistry panels are defined in Section 9.2 (pre-enrollment).

⁶ Genotyping may be performed on enrolled participants using cryopreserved PBMC collected at baseline.

⁷ Pregnancy test may be performed on blood specimens. Persons who are NOT of reproductive potential due to having undergone bilateral oophorectomy (verified by medical records), are not required to undergo pregnancy testing.

⁸ At an early termination visit for a withdrawn or terminated participant who is not HIV-infected (see Section 9.12), blood should be drawn for HIV diagnostic testing, as shown for visit 17 above. If a participant has a confirmed diagnosis of HIV infection, do not collect blood for HIV diagnostic testing (see Section 9.14).

⁹ Functional humoral assays may include nAb, ADCC, virion capture, and phagocytosis assays.

¹⁰ Syphilis testing will be done by serology.

¹¹ Chlamydia/Gonorrhea testing will be done with both rectal swabs and urine in males, and with urine and/or vaginal swabs in females; testing will occur at indicated visits and when clinically indicated.

¹² Cervical/vaginal swabs will be collected from females for bacterial vaginosis and *Trichomonas vaginalis* at the indicated visits and when clinically indicated.

¹³ Cervical/vaginal swabs will be collected from females for yeast only when clinically indicated.

¹⁴ Mucosal specimens will be collected once the participant has been found to have met mucosal specimen collection criteria specified in the SSP.

¹⁵ Mucosal biopsy collections must be at least 28 days from the previous biopsy collection.

¹⁶ The total 56-day blood collection includes 10mL maximum blood loss per biopsy collection visit.

¹⁷ And microscopy if needed.

¹⁸ Hormone panel (persons born female only) is defined in Sections 9.3 (enrollment visits) and 9.5 (follow-up visits).

¹⁹ The visit total indicates the total number of colorectal, cervical, or vaginal biopsies collected per visit.

²⁰ These biopsies will only be collected if the participant has missed prior collection visit(s), in order to maintain the overall number of biopsies in the "Total Biopsies" column.

²¹ For participants with confirmed diagnosis of HIV infection, only specimens required for protocol-specified safety laboratory tests, urinalysis and pregnancy tests will be collected.

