w = 5 x 1mL aliquots of ACD plasma will be harvested for storage during PBMC processing; no separate blood draw is needed.

y = SST blood collected for serum storage will also cover specimen needs for the VRC01 drug level, anti-VRC01 Ab level, and functional humoral assays; no separate blood draw is needed.

z = ACD blood collected for PBMC storage will also cover specimen needs for host genetics assay; no separate blood draw is needed.

TBD = to be determined.

Appendix I Laboratory procedures for Group 3

					Visit:	1	2	3	4	5	6	7	8	9	10	11	12	13	14	15	16	17	18	19				
					Day:	Screening	D-14	D0	D1-15	D29-43	D56	D57-71	D84	D85-99	D99-113	D112	D127-141	D168	D169-183 ¹⁵	D197-211 ¹⁵	D253-267 ¹⁵	D351-365 ¹⁵	D442-456 ¹⁵	D526-540 ¹⁵	Total			
					Week:	visit ¹	W-2	W0	W1-2	W5-6	W8	W9-10	W12	W13-14	W15-16	W16	W19-20	W24	W25-26	W29-30	W37-38	W51-52	W64-65	W76-77				
								Inf #1					Inf #2															
Procedure	Ship to ^{1,2}	Assay location ²	Tube Type ⁴	Tube size (vol. capacity) ⁴																					Total			
BLOOD COLLECTION																												
Screening/Diagnostic																												
Screening HIV test	Local lab	Local lab	SST	5mL	5	—	—	—	—	—	—	—	—	—	—	—	—	—	—	—	—	—	—	—	—	5		
HBsAg/anti-HCV	Local lab	Local lab	SST	5mL	5	—	—	—	—	—	—	—	—	—	—	—	—	—	—	—	—	—	—	—	—	5		
HSV-1/2	Local lab	Local lab	SST	5mL	—	5	—	—	—	—	—	—	—	—	—	—	—	—	—	—	—	—	—	—	—	5		
HIV diagnostics ⁸	UW-VSL/ HSML-NICD	UW-VSL/ HSML-NICD	EDTA	10mL	—	—	—	—	—	—	—	—	—	—	—	—	—	—	10	—	10	10	—	—	—	20		
Safety Labs²¹																												
CBC/Diff / platelets	Local lab	Local lab	EDTA	5mL	5	—	—	5	—	—	—	—	—	—	5	—	—	—	5	—	—	—	—	5	—	—	25	
Chemistry panel ⁵	Local lab	Local lab	SST	5mL	5	—	—	5	—	—	—	—	—	—	5	—	—	—	5	—	—	—	—	5	—	—	25	
Hormone Levels																												
Hormone panel ⁶	Local lab	Local lab	SST	8.5mL	—	8.5	—	—	—	—	—	—	—	—	—	—	—	—	8.5	8.5	8.5	8.5	8.5	8.5	8.5	8.5	60	
STI Serology																												
Syphilis ¹⁰	Local lab	Local lab	SST	5mL	5	—	—	—	—	—	—	—	—	—	—	—	—	—	—	—	—	—	—	—	—	—	5	
Drug Levels/Detection																												
VRC01 LS Ab levels	CSR	NVITAL/FHCRC	SST	8.5mL	—	y	—	y	y	—	—	—	y	—	y	—	—	y	y	y	y	y	y	y	y	y	0	
Immunogenicity Assays																												
Host genetics ⁹	CSR	FHCRC	ACD	8.5mL	—	z	—	—	—	—	—	—	—	—	—	—	—	—	—	—	—	—	—	—	—	—	0	
Anti-VRC01 LS Ab levels	CSR	VRC/NVITAL	SST	8.5mL	—	y	—	—	—	—	—	—	—	—	—	—	—	—	y	—	—	—	—	—	y	0		
Functional humoral assays ⁷	CSR	Duke	SST	8.5mL	—	y	—	y	y	—	—	—	—	—	y	—	—	—	y	y	y	y	y	y	y	0		

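### Apart from baseline and the final visit, anti-drug antibody is tested only 1-15 days after an infusion, when circulating drug can mask it in the bridging assay, so transient antibodies may be missed and onset cannot be dated

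*Protocol*

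**What the plan says.** **Assay.** Protocol 10.4.2 describes an electrochemiluminescence assay: "Serial dilutions of sera/plasma samples are incubated with optimized concentrations of biotinylated VRC01 and SULFO-TAG labeled VRC01". A signal needs one antibody to link a biotin-labelled and a SULFO-TAG-labelled drug molecule. The section says that the method is isotype-independent and "permits the detection of both high and low affinity antibodies". It does not mention drug tolerance, acid dissociation or how to read a negative when drug is present. For the LS variant, "The same assay format will be utilized for anti-VRC01LS, with reagents specific for that protein".

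**Schedule** (rows headed "Anti-VRC01 Ab levels" or the VRC01LS equivalent in the laboratory appendices):

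| Group | Baseline | Post-infusion test | Final test |
|---|---|---|---|
| 1, 2 (App. H) | Visit 2 | Visit 14 (D169-183) | Visit 17 (D351-365) |
| 3 (App. I) | Visit 2 | Visit 14 (D169-183) | Visit 19 (D526-540) |
| 4 (App. J) | Visit 3 | Visit 4 (D1-15) | Visit 14 (D169-183) |
| 5 (App. K) | Visit 3 | Visit 4 (D1-15) | Visit 17 (D351-365) |

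**Serum.** Footnote y of these appendices states that "SST blood collected for serum storage will also cover specimen needs for the VRC01 drug level, anti-VRC01 Ab level, and functional humoral assays". Protocol 9.4 also has serum collected before infusions for trough levels.

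**Analysis.** Anti-drug antibody is not named in any objective or endpoint in Protocol section 5. The SAP names it only in the heading of 8.6.2 and gives no method, table or reading rule.

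**The concern.** In a bridging format, unlabelled drug occupies the binding sites that the two labelled molecules need. Serial dilution does not simply remove the problem, because it dilutes antibody and drug together. The only result between baseline and study end therefore comes from serum with a high drug level, and nothing in the plan tells the analyst to qualify a negative.

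This matters for interpreting the PK. Serum VRC01 is a primary endpoint. SAP 8.5.2 computes trough and AUC accumulation after later infusions relative to the first, and terminal half-life after the last. Protocol 4.5.1 suggests that anti-drug antibodies might have speeded clearance in rats. If accumulation falls or half-life shortens in some participants, the team will want to know whether antibody was present at the time, and the current schedule may not be able to say.

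**Working it through.** **1. Visit alignment.** In the text available for review, some appendix rows have a surplus or missing column. The Appendix H row was aligned on the HIV-diagnostics row, whose 20 mL draw is fixed by its footnote: "blood should be drawn for HIV diagnostic testing, as shown for visit 17 above". The other appendices were aligned in the same way, on their own HIV-diagnostics and visit-total rows.

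**2. Time since infusion.**
- Groups 1-3, Visit 14: 169 - 168 = 1 to 183 - 168 = 15 days after the last infusion.
- Groups 4-5, Visit 4: 1 to 15 days after the only infusion (D0).
- Final test: 351 - 168 = 183 to 365 - 168 = 197 days (Groups 1-2); 526 - 168 = 358 to 540 - 168 = 372 (Group 3); 169-183 (Group 4); 351-365 (Group 5).

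**3. Projected VRC01.** The inputs are the HVTN 104 day-56 troughs (Protocol 4.7.1.3) and the 15-day half-life from VRC 602 (4.7.1.2). HVTN 104 used the same two doses: "In Group 5, the trough levels, measured before the second (day 56) and third (day 112) infusions, averaged 10.4 (6.8, 16.1) ug/ml" at 30 mg/kg, and 4.1 ug/mL at 10 mg/kg. Formula: C(d) = C(56) x 2^((56 - d)/15).

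| Days after infusion | 10 mg/kg (ug/mL) | 30 mg/kg (ug/mL) |
|---|---|---|
| 1 | 4.1 x 2^(55/15) = 52 | 10.4 x 2^(55/15) = 132 |
| 15 | 4.1 x 2^(41/15) = 27 | 10.4 x 2^(41/15) = 69 |
| 56 (observed trough) | 4.1 | 10.4 |
| 85 to 99 | 1.1 to 0.6 | 2.7 to 1.4 |
| 183 to 197 | 0.012 to 0.006 | 0.03 to 0.015 |

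A single exponential ignores the distribution phase, so the early values are probably low. From day 15 to days 85-99 drug falls 2^(70/15) = 25-fold to 2^(84/15) = 49-fold. For Group 4, the final test at 169-183 days has 0.06 to 0.03 ug/mL.

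**4. Sensitivity of step 3.**
- VRC 602 gives 35 and 57 ug/mL 28 days after 20 and 40 mg/kg. Interpolated to 46 at 30 mg/kg, day 15 is 46 x 2^(13/15) = 84 ug/mL, in line with 69.
- From the second HVTN 104 troughs (2.5 and 11.5), the window is 17-32 and 76-146 ug/mL.
- HVTN 104 also reports 4.2 and 11.9 ug/mL, described as 28 days after the third infusion. Taken literally, this gives 8-15 and 22-41 ug/mL in the window. That sits poorly with VRC 602, and with data running to day 168, which is 168 - 112 = 56 days after that infusion. Even so, drug in the window is well above the day-56 trough.

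**5. VRC01LS (assumption).** The protocol gives no human half-life, only a 2.5- to 3-fold increase in macaques. Take 37.5-45 days (2.5 to 3 times 15), and 60-75 days as a wider case, from 69-84 ug/mL at day 15:
- Days 85-99: about 15-29 ug/mL (37.5-45 days) or 26-44 ug/mL (60-75 days).
- Final test: about 0.1-0.5 or 1.1-3.8 ug/mL.

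**6. Effect on the assay (illustration only).** Assume retained signal = (2L/(2L + D/n))^2, where L is each labelled reagent in ug/mL, D is drug and n is the dilution factor. For L of 0.25-2 and n of 10-50 at 30 mg/kg:
- Days 1-15: from (0.5/(0.5 + 13.2))^2 = 0.1% to (4/(4 + 1.38))^2 = 55%.
- Days 85-99: from (0.5/(0.5 + 0.27))^2 = 42% to (4/(4 + 0.028))^2 = 99%.

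The direction is fixed, but the size depends on values that the documents do not give. Retained signal is also not a false-negative rate, which would depend on titre and on the positivity threshold.

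**The case against.** A reader might infer that antibodies arising during dosing would be reported as absent, or that the post-infusion result is worthless. The documents do not support either. The assay's tolerance is unknown and could be high. In Groups 1, 2 and 4 the final sample carries almost no drug, so a persistent antibody would still be found.

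Other points on that side also stand:
- Anti-drug antibody is not a listed endpoint, and Protocol 4.8 expects a low risk of immune reactions to a human antibody against a viral target. The clearance remark in 4.5.1 concerns rats.
- Faster clearance would still show in the measured drug levels. What is lost is attribution.
- Stored serum can be tested later, so nothing is irrecoverable.
- The window is not uniformly the peak: projected drug halves between day 1 and day 15. Nor is it strictly on-treatment, since it follows the last or only infusion.
- Moving the test to the Visit 13 trough looks attractive but is weaker. That visit has a single 8.5 mL tube, which also supplies a primary drug level. A trough before the last infusion cannot show a response to that infusion.

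None of this removes the gap. Between baseline and study end there is no low-drug test, and there is no rule for reading a negative taken in the presence of drug.

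**Conclusion.** The concern holds in limited form. The only post-infusion test before the final visit falls 1-15 days after an infusion. Projected VRC01 is then about 27-52 ug/mL (10 mg/kg) or 69-132 ug/mL (30 mg/kg), in an assay format open to drug interference and with no stated tolerance. A negative result there may be false; the rate cannot be computed. For VRC01, the exposure is confined to transient antibodies and to the timing of onset. For VRC01LS, the final sample is less reassuring, because residual drug depends on an unstated human half-life (about 0.1 to 3.8 ug/mL over the assumed range).

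The projections assume HVTN 104 troughs, a 15-day half-life and single-exponential decline. The safety and PK endpoints are not invalidated. What is weakened is the use of anti-drug antibody results to explain them.

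**What to change.** - **Appendices H and I:** add an anti-drug antibody test on stored Visit 16 serum, or move the Visit 14 test there. Visit 16 follows all infusions, has a 51 mL blood draw, and has projected VRC01 of about 0.6-1.1 ug/mL (10 mg/kg) or 1.4-2.7 ug/mL (30 mg/kg). Use Visit 13 trough serum only if volume remains after the primary drug-level assay.
- **Appendices J and K:** move the Visit 4 test to stored Visit 9 serum (days 85-99, 51 mL blood draw).
- **Protocol 10.4.2 and SAP:** state the assay's qualified drug tolerance. List serum drug concentration beside each anti-drug antibody result, and report a negative above that tolerance as inconclusive. This rule matters most for VRC01LS, where Visits 16 and 9 may still carry some 15-44 ug/mL (assumed half-lives as above).

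**Cost.** No new visit or blood draw. Keeping Visit 14 and adding Visit 16 means one more run per participant in Groups 1-3: 23 + 23 + 7 = 53 on the SAP's group sizes. Moving a test adds none, but leaves no anti-drug antibody result paired with the Visit 14 or Visit 4 biopsies.
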